Aim 1: To test CBT and Mindfulness/ACT intervention message efficacy for reducing momentary smoking urges (N=80). To inform just-in-time interventions, it is crucial to test if CBT and Mindfulness/ACT based messages can reduce momentary smoking urges. We will conduct a micro-randomized trial (repeated within-subject randomizations of messages) to accomplish this. In line with our existing protocol, participants first collect EMA data for 14 days, allowing us to determine high-risk situations for smoking. In the following intervention phase, participants receive tailored messages triggered by geofencing of participants' high-risk locations for a total of 30 days. Tailoring is based on established predictors of smoking relapse (stress and presence of other smokers). The micro-randomized trial tests the efficacy of CBT versus Mindfulness/ACT versus control messages for reducing smoking urge 15 minutes post message delivery. Secondary outcomes include smoking or other tobacco use (including e-cigarettes), affect, and stress.

Aim 2: To test if exposure to urge reduction messages results in changes in smoking behavior over time compared to an EMA only control group (N=80). It is important to investigate if repeated messages in the micro-randomized trial impact smoking behavior over time, in contrast to just repeated assessment without messages. Thus, this study includes a conventionally randomized clinical-trial component. Parallel to the micro-randomized trial group, a control group completes EMA surveys only without intervention messages. This allows us to test if messages reduce smoking behavior. The primary outcome is number of cigarettes per day at end of treatment, 3-, and 6-months follow-up. Secondary analyses explore biochemically verified 7-day point prevalence abstinence, switching to e-cigarettes, and other tobacco outcomes. Post-hoc dose-response analyses investigate the long-term efficacy of CBT or Mindfulness/ACT messages on smoking behavior.

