A total of N=80 participants will be randomized into an EMA-only control group, parallel to the micro-randomized trial intervention group (Figure: Study overview). This group will conduct 14-day EMA only training phase just like the micro-randomized trial group, but will not be switched over to the intervention phase after these initial 14 days. Instead, participants will continue the EMA-only data collection procedure for an additional 30-days (analogous to the 30-day intervention phase of the micro-randomized trial). During these 30 days, the EMA-only control group will continue to receive 3 randomly prompted EMA surveys per day and an additional 3 EMA surveys triggered by smoking reports. By comparing this control group to the micro-randomized trial intervention group, we will investigate if intervention message delivery results in changes in smoking behavior over time (see analytical strategy Aim 2).

Follow-up assessments

Follow-up assessment in both groups will be conducted at end of treatment (45 days), 3-months, and 6-months post-randomization. Surveys will be delivered online via Qualtrics and will assess current behavior (number of cigarettes/day, self-reported 7-day point prevalence abstinence), quit attempts, current quit motivation, frequency and intensity of smoking urges, and other substance use behavior including alcohol, cannabis, and other illicit drugs. Surveys will also assess baseline ACT measures: Avoidance and Inflexibility Scale and the FIT-60 (Flexibility Index Test).

Saliva cotinine will be used to **biochemically validate 7-day point prevalence abstinence** at each follow-up. Participants self-reporting smoking abstinence at any follow-up point will be mailed a saliva test-kit

(NicAlert test strip) and instructed to send one picture each of providing the saliva sample and the test kit result. We will only receive pictures of the test process and result and not receive an actual saliva sample. The picture of the test process (participant providing the saliva sample) will be used to confirm that the participant provided the sample him- or herself.

2. Describe the number and type of study visits and/or contacts between the study team and the participant, how long they will last, and where/how they will take place.

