Aim 2 analyses will use data from both the micro-randomized trial group (N=80) and the EMA control group (N=80). **Primary outcome:** The primary outcome will be self-reported number of cigarettes/day in the past week at 45-day, 3-, and 6-month follow-up. GEE will examine cigarettes/day at each follow up by group (micro-randomized trial vs. EMA-only control). Independent variables are group membership, variables that differ by group at baseline, gender, and nicotine dependence. Again, **multiple imputation procedures** will be used to impute missing data at follow-up.

Analytical strategy Aim 3: Explore moderation effects of substance co-use (cannabis, alcohol, other drugs) and exposure to specific location (home, work, bars) on urge reduction message efficacy.

Based on our data on high co-use of cigarettes with cannabis and alcohol, as well as changes in perceived reward of smoking cigarettes when under the influence of cannabis or alcohol, analyses in this aim will explore if message efficacy is moderated by substance co-use (whether a participant currently is under the influence of another substance, e.g., cannabis, alcohol, other drugs). Centered and weighted least squares

models¹⁵² similar to those for Aim 1 will be estimated with predictors intervention message type (CBT, Mindfulness/ACT, control), substance use (cannabis, alcohol, other drugs, none), and their interaction. Based on existing evidence on alcohol and cannabis co-use as barrier to cigarette smoking cessation, we hypothesize that intervention message efficacy will be reduced when participants are under the influence of another substance. However, analyses for this aim will enable us to explore if specific types of messages (CBT, Mindfulness/ACT, and subconstructs) are more helpful in co-use situations.

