Moreover, we will explore aspects of intervention message-situation fit. We will test if specific locations (e.g., home, work, bars) impact intervention message efficacy. Mixed models will be estimated containing the predictors intervention type (CBT, Mindfulness/ACT, control), location (home, work, bar, other locations), and their interaction. We will explore other situational characteristics and intervention message-situation fit based on affect, arousal, stress, and the presence of other smokers. We do not have specific hypotheses about moderation effects of location and other situational characteristics, but findings will inform future interventions using adaptive messages over time to improve intervention-message situation fit and intervention efficacy.

5. Answer the following if they are relevant to your study design:

- A. If the study has different arms, explain the process for assigning participants (intervention/control, case/control), including the sequence and timing of the assignment.

We will use stratified block randomization to assign participants into the micro-randomized trial intervention group (N=80) and EMA-only control group (N=80). The stratification variable known to robustly impact smoking cessation success will be level of nicotine dependence (smoking within first 30 mins after waking, y/n).¹³¹ Gender will be used as additional stratification variable. We will generate a randomization table and participants will be assigned after baseline completion.

- B. If human biospecimens (blood, urine, saliva, etc.) will be collected, provide details about who will collect the specimen, the volume (ml) and frequency of collection, how the specimen will be used, stored, identified, and disposed of when the study is over. If specimens will be collected for use in future research (beyond this study), complete the “Biospecimen Repository” section below.

N/A

- C. If genetic/genomic analyses are planned, address whether the data will be contributed to a GWAS or other large dataset. Address returning unanticipated incidental genetic findings to study participants.

N/A

- D. If clinical or laboratory work will be performed at JHU/JHH, provide the JH Biosafety Registration Number.

N/A

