- E. If you will perform investigational or standard diagnostic laboratory tests using human samples or data, clarify whether the tests are validated and/or the lab is certified (for example is CLIA certified in the U.S.). Explain the failure rate and under what circumstances you will repeat a test. For all human testing (biomedical, psychological, educational, etc.), clarify your plans for reporting test results to participants and/or to their families or clinicians. Address returning unanticipated incidental findings to study participants.

N/A

F. If your study involves medical, pharmaceutical or other therapeutic intervention, provide the following information:

a. Will the study staff be blind to participant intervention status?

No

b. Will participants receive standard care or have current therapy stopped?

No

c. Will you use a placebo or non-treatment group, and is that justifiable?

Yes, control group will receive no intervention messages and only complete mobile surveys on their phones. This decision is defensible, since most smokers never receive evidence-based smoking cessation interventions and previous studies have demonstrated that if anything, repeated assessments of smoking on mobile devices result in lower cravings.

Moreover, self-monitoring of smoking behavior is a standard component of evidence-based smoking cessation counseling. Therefore, the data collection activities the control group undertakes may result in reduced smoking urges and smoking behavior over time.

If requested, participants in both conditions request more intensive smoking cessation support outside of the study, they will be offered additional telephone counseling by the PI or referred to the Smokers Quitline ([name]).

d. Explain when you may remove a participant from the study.

In the unlikely event that participants are significantly distressed by any aspect of their study participation, they will be offered the opportunity to discuss these issues with a PhD psychologist and smoking cessation counselor ([name], PI). If participants request more intensive smoking cessation support, they will be offered additional telephone counseling by the PI or referred to the Smokers Quitline ([name]).

e. What happens to participants on study intervention when the study ends?

Participants will be referred to the Smokers Quitline ([name]) if they desire additional smoking cessation support.

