- d. Will the data be stored on a secure server (@JHSPH/on-site)? Yes No

- e. Will the data be stored in the Cloud/Web? Yes No

- f. Will it be encrypted? Yes No

- g. Will you be backing up your data? Yes No

3. Mobile Apps Yes No

FOR STUDIES USING MOBILE APPS: When the use of a mobile app is approved solely for a research use, the IRB either requires that it be restricted to people who consented to the research, or when a screen/script is used, for participants to understand that this is not a medical tool or a public app, but is for use only in a research study only. Please check the appropriate box(es) below that describe your study:

- Use of the app is restricted to people in the research, with access limited to those who have consented to the study.
- The consent information for participants clarifies that the app is not for clinical or public use but is restricted to this research study

4. Audio Recording: Yes No

If yes, please answer the following:

- a. Will you store the audio recording securely in a locked cabinet/room until transcription is complete? Yes No

- b. Will you use a transcription service? Yes No

**If yes, if the PII comes from JHH/JHHS, you must use an approved vendor; otherwise, be aware of the data security protections that the transcription service provides.*

- c. Will the audio recording be destroyed immediately after transcription? Yes No

If no, why not? How long will it be retained?

4. **Photograph/Video:** Yes No

If yes, please answer the following:

- Will the photographs/videos be stored securely in a locked cabinet or room? Yes No
- Will the photograph/video be destroyed? Yes No

If yes, when?

The picture of the participant's ID will be destroyed at the end of the study when all study activities have been completed. The ID document will subsequently be deleted after validation of participant details. Only the participant picture (headshot) on the ID will be retained for biochemical verification of smoking abstinence. The participant picture needs to be retained until the end of the study to verify that the participant provided the saliva sample for biochemical verification of smoking status. The picture of the participant providing a saliva sample will be destroyed as soon as we have confirmed the identity of the participant by comparing it to the ID picture of the participant on file. The participant picture on file will be deleted at the end of data collection.

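### In the 80 vs 80 comparison, verified abstinence rests on judging participant-sent pictures, with staff not blind to arm and no written cut-off or masked reading

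*Combined protocol and SAP*

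**What the plan says.** **Verification.** V.C.1 (Follow-up assessments) has anyone who reports abstinence at a follow-up mailed a NicAlert strip and "instructed to send one picture each of providing the saliva sample and the test kit result". There is no laboratory back-up: "We will only receive pictures of the test process and result and not receive an actual saliva sample". The picture of the sample being given serves to confirm identity. Under Photograph/Video in VI.B, the rule for that picture reads: "destroyed as soon as we have confirmed the identity of the participant by comparing it to the ID picture of the participant on file". By contrast, the ID headshot is kept until data collection ends.

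**Blinding.** V.C.5.F.a asks "Will the study staff be blind to participant intervention status". The answer is a bare No, with no exception for outcome assessment.

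**Status of the outcome.** Section I, Aim 2: "Secondary analyses explore biochemically verified 7-day point prevalence abstinence, switching to e-cigarettes, and other tobacco outcomes". The Aim 2 primary outcome in V.C.4 is different: "The primary outcome will be self-reported number of cigarettes/day in the past week at 45-day, 3-, and 6-month follow-up".

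**What is absent.** The plan does not state which strip level counts as abstinent, how an unclear or unreadable picture is classed, or who reads the strip. It describes no masked reader, second reader or adjudication step.

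**The concern.** Participants know whether they receive messages, so self-reported smoking in the randomized comparison can be coloured by that knowledge. The strip is the only biochemical check on self-report in Aim 2. It is useful to the extent that its reading does not depend on the arm. Here it involves two human judgements from pictures: is the strip negative, and does the face match the headshot? If the person deciding an unclear picture knows the arm and has no fixed rule, part of that independence is lost. Participants cannot be masked to receiving messages, but the reader of a picture can be masked to arm.

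**Working it through.** The plan gives no figure on this point, so there is nothing to reproduce. The first three steps set the sections side by side; the last two give a size under stated assumptions.

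**1. Who judges the pictures.** V.C.1 says that the team receives them. VI.B says that the team confirms identity. No laboratory or outside reader appears anywhere. That study staff also read the strip is therefore an inference, though a natural one.

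**2. What the reader may know.** V.C.5.F.a leaves staff unblinded. Coding by study ID (VI.C) hides the name, but nothing says that it hides the arm. Staff could also learn the arm through compliance check-ins (V.C.2) or through the telephone counseling offered on request (V.C.5.F).

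**3. Where it applies.** The two arms have 80 participants each (V.C.5.A), with strips possible at 45 days, 3 months and 6 months. The N=10 pilot has no described control arm and, of the follow-up surveys, only the 45-day one (V.C.1, V.C.3), so reading cannot differ by arm there.

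**4. Simple illustration.**
- One decision: 1/80 = 1.25 points on an arm's verified rate.
- Assumption: 10-15% report abstinence at a follow-up, so 0.10 × 80 = 8 to 0.15 × 80 = 12 strips per arm.
- Assumption: two pictures per arm are unclear, i.e. 2/12 = 17% to 2/8 = 25% of strips.
- Any single rule applied to both arms adds 2 and 2, or 0 and 0. Calling them in opposite directions adds 2 and 0. The spurious difference is 2/80 = 2.5 points.
- With one or three unclear pictures per arm it is 1/80 = 1.25 or 3/80 = 3.75 points.

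**5. Wider range.** Spurious difference = share reporting abstinence × share of strips unclear × difference between arms in calling an unclear strip negative. All three are assumptions. The false-positive rates come from exact binomial enumeration of a two-sided pooled z-test at 0.05, with 80 per arm and true rates equal. They further assume that 60% of clear strips are negative and that calls on unclear strips are centred on 50%. Without differential reading the rate is 0.047-0.048.

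| Reporting abstinence | Unclear | Calling difference | Spurious difference | False-positive rate |
|---|---|---|---|---|
| 15% | 10% | 25 points | 0.4 points (0.3 of 80) | 0.048 |
| 25% | 30% | 50 points | 3.8 points (3 of 80) | 0.10 |
| 15% | 10% | 100 points | 1.5 points (1.2 of 80) | 0.06 |
| 25% | 30% | 100 points | 7.5 points (6 of 80) | 0.27 |

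The last two rows need every unclear strip called negative in one arm and none in the other. The last row also needs six unclear strips per arm.

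**The case against.** The strongest reply is that little is at stake. Verified abstinence is exploratory, and strip reading touches neither cigarettes per day nor momentary urge. Clear strips still refute false claims of abstinence, so only unclear pictures are open to judgement, and no section says that such pictures are expected. The staff-blinding answer is one word to a general template question; it does not say that the arm is in view when a picture is read. All of this stands, and it limits the point to a minor one. It does not remove it, because nothing in the plan keeps the arm from the reader or fixes the rule.

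A reader might also infer more than the documents support:

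- **A 5-point distortion from two unclear pictures per arm.** Against a common rule the difference is 2.5 points. Reaching 4/80 = 5 points needs the further assumption that both accepted claims are false and both rejected claims are true.
- **That the strip can never be re-read.** VI.B destroys the sample picture once identity is confirmed. No section schedules destruction of the strip picture, and that sentence does not cover sample pictures where identity was not confirmed. Only confirmed identity matches become uncheckable.
- **That verification guards the primary outcome.** It checks claims of abstinence only, so a flaw in it does not spread to cigarettes per day.

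**Conclusion.** The point holds as a minor design weakness. Staff are stated to be unblinded, the outcome depends on judging pictures, and neither a cut-off nor a masked reading is given, so unclear pictures could be judged differently by arm. The documents do not show that they would be. About 2.5 points is a fair illustration for two unclear pictures per arm called in opposite directions; set against an assumed 10-15% reporting abstinence, that is a sixth to a quarter of the rate. The share reporting abstinence, the share of unclear pictures and the size of any difference in calling are all assumptions, and the effect is small unless unclear pictures are common. The conclusion also rests on the inference that the study team reads the strips.

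**What to change.** State in V.C.1 and V.C.5.F.a that:

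- strip and identity pictures are filed by study ID without the arm;
- an existing team member reads them, with the arm field hidden, against a cut-off fixed in writing beforehand, which also says how an unreadable picture is counted;
- the reading is recorded and locked before the sample picture is destroyed.

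The cost is a file-naming and access rule and a few sentences of text. It needs no extra staff, adds nothing for participants, and leaves the privacy-driven destruction of the sample picture in place. The downside is that in a small team the reader may sometimes recall a participant's arm, so masking will be imperfect; the written cut-off helps in those cases too.

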Aim 3 will explore moderation effects of substance co-use (cannabis, alcohol, other drugs) and exposure to specific locations (home, work, bars) on urge reduction message efficacy among intervention group participants.

- B. Provide a sample size and a justification as to how you arrived at that number. If you use screening procedures to arrive at a final sample a table may be helpful.

Message acceptability: A sample size of 300 participants receiving 10 randomized messages will yield 3,000 exposures. Given that we are testing 124 messages across 3,000 exposures, each message will have an average of 24.2 completed assessments. Kim et al. (2019) demonstrated that 25 evaluations per message is sufficient to estimate message acceptability by balancing accuracy and efficiency. Of the 10 randomly delivered messages, each participant will provide open-ended feedback on a random set of two of the messages. Thus, qualitative feedback will be given for 600 exposures or an average of 4.8 open-ended responses per message.

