To assess understanding of the information provided in the informed consent, eligible participants will be asked a series of three multiple-choice questions regarding the informed consent before being able to proceed with

the study. Answers will be collected and any wrong answer will result in the potential participant being prompted to review the full consent document before attempting the consent questions again. Potential participants will not be enrolled in the study if they answer the questions incorrectly four times.

- e. Whether you will obtain a legally authorized representative's signature for adults lacking capacity:

N/A

- f. If children are included in the study, if and how you will obtain assent from them:

N/A

- g. If children are included in the study, how you will obtain permission for them to participate from their parent, legal guardian, or other legal authority (if child is in foster care or under government supervision):

N/A

- h. If you are seeking a waiver of informed consent or assent, the justification for this request:

N/A

- i. Whether you will include a witness to the consent process and why:

N/A

- j. If the language is unwritten, explain how you will communicate accurate information to potential participants and whether you will use props or audio materials:

N/A

2. Identify the countries where the research will take place, and the languages that will be used for the consent process.

Country	Consent Document(s) (Adult Consent, Parental Permission, Youth Assent, etc.)	Languages
United States	Adult consent	English

C. **Study Implementation:**

1. Describe the procedures that participants will undergo. If complex, insert a table below to help the reviewer navigate.

Message acceptability testing

After informed consent, participants will be asked survey questions via Qualtrics on demographic information, smoking and tobacco use behaviors, and quit attempt history. The Avoidance and Inflexibility

Scale will measure the person's willingness to experience negative thoughts and affect. Message acceptability will be measured through four Likert-scale questions on message content, design, helpfulness for reducing smoking urges, and helpfulness for helping with quitting smoking. These will be asked for 10 randomly selected messages for each participant. Participants will complete open-ended feedback on two of the 10 randomly selected messages.

All other study phases and procedures

Training phase - EMA data collection

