Analyses for message acceptability testing will utilize a mixed methods approach. For the quantitative analyses, the **primary outcome** will be message acceptability expressed as the average score of Likert responses to helpfulness to cope with smoking urges or craving and to support quit attempts and acceptability of message content and design. Messages will be ranked by score and messages with low scores will be either modified in line with qualitative participant feedback or removed before moving to the next study phase. Analyses assessing message acceptability across age, gender, and race/ethnicity will include independent variables age, gender, race/ethnicity, educational attainment, psychological flexibility, smoking frequency, quit motivation, and past quitting attempts. These quantitative analyses on message acceptability will be supplemented with qualitative analyses involving inductive and deductive coding of participants' open-ended responses to inform how messages should be modified.

Analytical strategy Aim 1: To compare CBT and ACT intervention message efficacy.

Aim 1 analyses to test the hypothesis of a proximal benefit of urge reduction messages will be conducted using a centered and weighted least squares method, which estimates treatment effects and allows inclusion of covariates. The method is similar to GEE and multi-level models in that it accounts for dependence of responses within individuals due to repeated measures via the use of robust standard errors. Moreover, the method takes advantage of the sequential randomization to estimate causal treatment effects. The **primary outcome** will be participants' rating of **smoking urge** in EMA-post surveys, prompted 15 minutes after intervention message delivery, and controlling for the ratings in EMA-pre surveys. The main independent variable will be message type: **CBT versus Mindfulness/ACT versus a Control Message** ("Thank you for completing the survey"). We will also **test differences in efficacy between CBT versus Mindfulness/ACT**. We will use **multiple imputation** to impute missing data in EMA-post surveys.

Analytical strategy Aim 2: To test if urge reduction messages change smoking behavior over time.

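### Messages are ranked on unadjusted mean scores although each is rated by a nearly separate set of people, so rater leniency adds removable noise to the choice of messages

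*Combined protocol and SAP*

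**What the plan says.** Section III.B sets the size of the survey: "A sample size of 300 participants receiving 10 randomized messages will yield 3,000 exposures". With "testing 124 messages across 3,000 exposures, each message will have an average of 24.2 completed assessments", the plan relies on a cited source for the view that "25 evaluations per message is sufficient to estimate message acceptability by balancing accuracy and efficiency". Section V.C.1 (Message acceptability testing) describes the allocation of the four Likert questions: "These will be asked for 10 randomly selected messages for each participant".

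Section V.C.4 (Analytical strategy Message Acceptability) defines the primary outcome as "message acceptability expressed as the average score of Likert responses to helpfulness to cope with smoking urges or craving", together with the items on quit support, content and design. It then states the decision rule: "Messages will be ranked by score and messages with low scores will be either modified", guided by the open-ended comments, or removed. This happens before the next study phase. No cut-off is given.

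The same section lists covariates, but for a different purpose: "Analyses assessing message acceptability across age, gender, and race/ethnicity will include independent variables age, gender, race/ethnicity, educational attainment" and further participant characteristics. Neither that list nor the ranking step contains a rater effect, within-rater centring or a mixed model.

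**The concern.** This is an incomplete design, because a rater sees 10 of 124 messages and two messages are mostly judged by different people. Some people score everything high and others score everything low. A message that happens to draw lenient raters moves up the list for reasons unrelated to its content. Because messages are chosen at random, no message is systematically favoured, so the problem is variance only.

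That variance is avoidable. The nine other scores from each rater show how lenient that rater is, and the ranking as described does not use them. The ranking feeds the decision on which messages are revised or removed before the efficacy trial. A noisier list flags more sound messages and lets more weak ones through.

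**Working it through.** **Inputs from the documents.** Raters R = 300, messages per rater K = 10, messages M = 124.

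**The plan's own figure.** Ratings per message: r = 300 × 10 / 124 = 24.19, which reproduces the stated 24.2.

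**Overlap of raters.** Expected raters shared by two given messages: 300 × (10/124) × (9/123) = 1.77, out of about 24 each. The rater sets are nearly disjoint.

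**Assumed inputs.** Score = message effect + rater leniency + residual, with within-message variance set to 1. The rater share of it, ρ, is not in the documents and is varied from 0 to 0.5. Between-message variance is taken as 0.02 or 0.05. The worst quarter (31 of 124) stands in for the unstated cut-off.

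**Error variance, treating the design as balanced.**
- Unadjusted mean: (1/r) × [1 − ρ(K−1)/(M−1)].
- Rater-adjusted: 1 / { r × [E/(1−ρ) + (1−E)/(1−ρ+Kρ)] }, where E = M(K−1)/[K(M−1)] = 124 × 9 / (10 × 123) = 0.907.
- Example, ρ = 0.35: unadjusted (1/24.19) × (1 − 0.35 × 9/123) = 0.0403. Adjusted 1 / {24.19 × [0.907/0.65 + 0.093/4.15]} = 0.0291. Ratio 1.38.

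**Simulation of the planned survey.** 300 raters each score 10 random messages of 124, with at least 120 simulated surveys per setting. Unadjusted means are compared with message effects from a model with a random rater effect. Ranges cover repeated runs, including runs in which ρ was estimated from each simulated survey.

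| ρ | Ratio, formula | Ratio, simulated | Worst quarter found, message variance 0.02 | Worst quarter found, message variance 0.05 | Extra found, of 31 |
|---|---|---|---|---|---|
| 0 | 1.00 | 1.00 | no change | no change | 0 |
| 0.1 | 1.05 | 1.05 | about the same | about the same | 0.3 or less |
| 0.2 | 1.15 | 1.14–1.17 | 0.52 → 0.53–0.54 | 0.63–0.64 → 0.64–0.66 | about 0.5 |
| 0.35 | 1.38 | 1.36–1.43 | 0.52 → 0.55 | 0.63–0.64 → 0.66–0.67 | 1.2–1.4 |
| 0.5 | 1.76 | 1.74–1.86 | 0.52 → 0.58–0.60 | 0.63–0.64 → 0.69–0.72 | 2.0–2.5 |

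The upper ends of the simulated ratios arise when ρ is expressed as a share of total rather than within-message variance. In precision terms, adjustment at ρ = 0.35 is worth 24.2 × 1.38 ≈ 33 ratings per message with nobody added.

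**The case against.** The strongest objection is that the gain in actual decisions is small. A variance ratio of 1.4 sounds large, but it moves little more than one message in 31, and at a rater share of 0.1 it moves almost none. Most misclassification comes from residual noise at about 24 ratings per message and remains after adjustment. With message variance 0.02, even the adjusted ranking misses 40% or more of the worst quarter. All of this stands and limits the importance of the point.

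Low scorers may also be revised instead of removed, with open-ended comments as a guide. That softens the effect of a wrong rank, although 600 / 124 ≈ 4.8 comments per message is thin support.

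The plan never says that the message score is unadjusted, and the section is meant to be brief. An average Likert score with no adjustment stated is still most naturally read as a plain mean. The cited benchmark of 25 evaluations might already allow for rater variance. That cannot be checked from the documents, and it would not change the fact that adjustment gives more precision from the same ratings.

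Finally, a mixed model requires a choice about how message effects are estimated, and its scores are a little less transparent to message writers. These costs are minor.

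**Conclusion.** The concern holds as an efficiency point of low severity. As described, the ranking leaves rater leniency in the message scores although the design allows most of it to be removed. The penalty is an error variance about 1.15 to 1.8 times larger than necessary for rater shares of 0.2 to 0.5, and negligible at 0.1 or below. In no setting examined was the adjusted ranking worse, and at zero rater share the two were equal. The size rests on the assumed rater share, message variance and worst-quarter cut-off, none of which the documents supply; the direction does not. Message scores remain unbiased, and the Aim 1 and Aim 2 inferences are not affected.

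**What to change.** In Section V.C.4, state that messages will be ranked on their estimated effects from one linear mixed model. The outcome would be the average of the four Likert items at each exposure, with an effect for each message and a random intercept for rater. Report the estimated rater variance so that readers can see how much the adjustment mattered. If it is near zero, the ranking will be practically the same as the one from plain means. The cost is one extra model on ratings that the survey collects anyway, with no added participants or questions. If the survey has already been run, the model can still be fitted to the existing data, although the choice of messages may by then be fixed.
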